#### 2.7.2.1.2 Analysis of uncorrected ACPR using Kaplan-Meier method

For the FAS, the proportion of patients with uncorrected ACPR at Day 29 and 95% CI will be also estimated using the Kaplan-Meier method ([Stepniewska and White 2006](#) and [WHO 2015](#))

**Event** = PCR-uncorrected non-responder during the study (same as at Day 29, See Section 2.1). The event time is the first time when the patient becomes a non-responder without PCR-correction. If a patient parasitaemia is not cleared at all, Day 7 is considered as the event time.

The uncorrected ACPR rate at Day 29 is estimated by the survivor function at Day 29.

##### **Rule for censoring:**

The following censoring rules will be applied to the patients who were not non-responders

- Patients who received non-rescue anti-malaria medication will be censored at the first time of anti-malaria medication;
- other patients will be censored at the time of last parasitemia assessment.

### **2.7.2.2 Treatment failure related parameters**

For the following parameters, 95% confidence intervals will be provided for each treatment group by cohort using the Pearson-Clopper method:

- proportion of patients with parasitaemia at 12, 24, and 48 hours after treatment
- proportion of patients with ETF
- proportion of patients with LCF
- proportion of patients with LPF

The above parameters will be determined using the uncorrected parasite counts.

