5.5.6 Rescue medication

The following circumstances warrant discontinuation of study treatment and the implementation of rescue medication (see [Section 6.5.8](#)):

Early treatment failure (ETF)

ETF is defined within this protocol as:

1. Clinical decline or lack of improvement (per Investigator) at 24 hours after first dose of treatment.
2. Development of any clinical complications (described in the WHO definition of complicated/severe malaria (WHO Guidelines 2010)) in the presence of parasitaemia within 72 hours of the first dose of treatment
3. Parasitaemia $> 75\ 000/\mu\text{L}$ at or after 12 hours post-dose
4. Parasitaemia \geq baseline with or without fever at 36 hours after first dose of treatment
5. Any parasitaemia based on microscopy with fever, 48 hours post-dose
6. Parasitaemia $> 100/\mu\text{L}$ based on microscopy with or without fever, 72 hours post-dose

Late Clinical Failure (LCF)

Development of danger signs or severe malaria on any day between Study Day 5 and Day 29 in the presence of parasitaemia without previously meeting any of the criteria of ETF.

Presence of parasitaemia and axillary temperature $\geq 37.5^\circ\text{C}$ on any day between Study Day 5 and Day 29 without previously meeting any of the criteria of ETF.

Late Parasitological Failure (LPF)

Presence of parasitaemia on any day between Study Day 5 and Day 29 and axillary temperature $< 37.5^\circ\text{C}$ without previously meeting any of the criteria of ETF or LCF.

Commencement of rescue medication with Coartem may occur after start of trial medications and up to Study Day 28 as deemed necessary by the investigator. Any patient on KAE609 who

did not need rescue medication up to Study Day 28, will be given Coartem at end of the study at Study Day 29. Rescue medication according to local guidance will be used for severe malaria.

Patients randomized to Coartem and meeting treatment failure definition will be further treated by rescue medication as per local treatment guidance.

The patients receiving rescue medication will not be replaced and will not discontinue the study (i.e., all the examinations as per the assessment schedule and all CRF pages for this patient will need to be completed).

Safety blood tests (Full Blood Count (FBC) and blood chemistry) will be collected on the initial day of rescue medication dosing. Blood films and blood sampling for parasite count and genotyping must be taken before giving the rescue treatment.

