9.5.1.2 Treatment failure related parameters

For the following parameters, 95% confidence intervals will be provided for each treatment group by cohort using the Pearson-Clopper method:

- proportion of patients with parasitaemia at 12, 24, and 48 hours after treatment
- proportion of patients with ETF
- proportion of patients with LCF
- proportion of patients with LPF

The above parameters will be determined using the uncorrected parasite counts.

In addition, patients whose outcome status cannot be determined due to incomplete/missing data will be excluded from analysis.

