### **2.7.1 Secondary endpoints**

All efficacy analyses are secondary. Secondary efficacy variables include:

- PCR-corrected ACPR at Study Days 15 and 29;
- Uncorrected ACPR at Study Days 15 and 29;

- Proportion of patients with parasitaemia at 12, 24, and 48 hours after the first dose of study drug;
- Parasite clearance time (PCT), defined as time from the first dose until the first total and continued disappearance of asexual parasite forms which remained at least a further 48 hours;
- Fever clearance time (FCT), defined as time from the first dose until the first time the axillary body temperature decreased below and remained below 37.5°C axillary or 38.0°C oral/tympanic/rectal for at least a further 24 hours;
- Proportion of patients with ETF;
- Proportion of patients with LCF;
- Proportion of patients with LPF;
- Incidence rate of recrudescence and reinfection at Study Day 29.

Analyses of ACPRs (PCR corrected or uncorrected) will be based on the FAS and PPS. Analyses of other secondary efficacy variables will be based on the FAS.

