### **Handling of missing values/censoring/discontinuations**

Patients whose outcome status cannot be determined due to incomplete/missing data will be excluded from analysis. Especially, the denominator is the number of patients who experience treatment failure or have malaria blood film result at Day 29 for LCF and LPF. Patients with ETF will be excluded from the analysis of LCF and patients with ETF or LCF will be excluded from the analysis of LPF.

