### **Handling of missing values/censoring/discontinuations**

Patients without parasite clearance for whatever reason will be censored at the time of last parasite assessment.

Patients who did not have fever at baseline will not be included in the analysis of FCT. Patients without fever clearance for whatever reason will be censored at the time of last temperature assessment.

In case that a patient receives rescue medication before (parasite or fever) clearance, the time to event will be censored at the first use of rescue medication.

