**Table 5-7 Rules for flagging variables**

Timing of measurement	Type of data	Rule
Baseline	All data	The last measurement made prior to and including administration of the first dose of study treatment – note this may include measurements taken on the day of randomization. If a patient did not receive any dose of study treatment then the randomization date will be used.
Post-baseline efficacy	All data	The measurement closest to the target day/time will be used. In the event that two measurements are taken equally apart (e.g. 1 day before target date and 1 day after) the first one will be used.
Post-baseline safety	Summary visit information (e.g. lab, ECG, etc.)	The measurement closest to the target day/time will be used. In the event that two measurements are taken equally apart, the first one will be used.
Post-baseline safety	Notable abnormalities (e.g. lab, ECG, VS)	The most extreme measurement in the window will be used. Note this means a patient can have a notably high and notably low measurement within a window

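### No rescue rule is stated for the proportion with parasitaemia at fixed hours, so a film cleared by Coartem rescue can count as parasite-free under a KAE609 dose, essentially at 48 h

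*SAP*

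**What the plan says.** **The endpoint.** SAP 2.7.2.2 lists the "proportion of patients with parasitaemia at 12, 24, and 48 hours after treatment", with exact 95% confidence intervals by arm. On the data to use, Protocol 9.5.1.2 says "The above parameters will be determined using the uncorrected parasite counts"; the SAP repeats this.

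**The rules that decide which patients and films enter.**
- Analysis set (SAP 2.7.1): "Analyses of other secondary efficacy variables will be based on the FAS". The FAS is by randomised arm and does not remove rescued patients.
- Exclusions (SAP, missing-data paragraph after 2.7.2.2): "Patients whose outcome status cannot be determined due to incomplete/missing data will be excluded from analysis". Rescue is not mentioned.
- Choice of film (SAP Table 5-7, post-baseline efficacy): "The measurement closest to the target day/time will be used". Table 5-6 sets the parasite-count windows at over 10 to 18 h, over 18 to 30 h and over 42 to 54 h for the 12, 24 and 48 h time points.

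**Rescue.** Under Protocol 5.5.6, rescue can begin at any time after study drug has started. One early-failure criterion is "Clinical decline or lack of improvement (per Investigator) at 24 hours after first dose of treatment". Others concern high density from 12 h, density at 36 h not below baseline, and complications within 72 h. Rescued patients stay in the study and complete the assessment schedule. A film must be taken before rescue is given.

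**Neighbouring endpoints.** For parasite and fever clearance times (SAP 2.7.2.3), if rescue precedes clearance, "the time to event will be censored at the first use of rescue medication". Protocol 9.5.1.1 counts patients rescued for *P. falciparum*, other than for a new infection, as treatment failures in ACPR.

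**The concern.** The plan handles rescue explicitly for clearance times and, in the protocol, for ACPR, but not for the fixed-hour proportions. The missing-data rule does not fill the gap, because a film taken after rescue is present and readable. The closest-measurement rule then selects it like any other film.

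Two outputs on early parasite clearance can therefore disagree about one patient. Someone positive at 36 h, rescued, and negative at 48 h is censored as not cleared in the clearance-time analysis, yet counts as free of parasites at 48 h under the assigned KAE609 dose. The direction favours KAE609. The arms most exposed are those where early failure is most likely, and Protocol 3.1 expects sub-therapeutic efficacy in Cohorts 1 and 2. A reader using the 48 h proportion to compare doses could not tell which negative films reflect KAE609 and which reflect Coartem.

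**Working it through.** The documents give no expected rate, power or precision for this endpoint, so there is no plan figure to reproduce. The check is a reading of the rules, followed by an illustration of size.

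**Step 1. Can rescue precede each film?**
- *12 h.* The density criterion starts at 12 h. Only an early complication, investigator discretion or a twice-vomited KAE609 dose (Protocol 5.5.4) can put rescue earlier. Close to nil.
- *24 h.* A patient failing the 24 h clinical criterion has a film before rescue at about that time. Earlier rescue needs one of the routes above, or density above 75 000/µL between 12 and 24 h from an entry ceiling of 50 000/µL. Rare.
- *48 h.* Rescue after the 24 h or 36 h criterion precedes the 48 h film. The film taken before rescue falls in the 24 h window (over 18 to 30 h) or the 36 h window (over 30 to 42 h), so the 48 h window picks up the later film.
- *Failures first met at 48 h or 72 h.* All three counts precede rescue and are tabulated correctly.

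**Step 2. Size of the difference.** In an arm of *n*, let *u* be the unrescued patients positive at 48 h, *x* the patients rescued before 48 h whose last film before rescue was positive, and *y* those of the *x* who are negative at 48 h.
- As written: (*u* + *x* − *y*)/*n*
- By last film before rescue: (*u* + *x*)/*n*
- Difference: *y*/*n*

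Each such patient therefore moves the proportion by 1/10 = 10 percentage points in an arm of 10, and by 1/20 = 5 points in an arm of 20.

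**Step 3. Illustrations, all assumed, with *u* = 0 and *n* = 10 (Clopper-Pearson 95% intervals).**

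| *x* | *y* | As written | By last film before rescue |
|---|---|---|---|
| 1 | 1 | 0% (0 to 30.8) | 10% (0.3 to 44.5) |
| 2 | 2 | 0% (0 to 30.8) | 20% (2.5 to 55.6) |
| 4 | 0 | 40% (12.2 to 73.8) | 40% (12.2 to 73.8) |
| 4 | 2 | 20% (2.5 to 55.6) | 40% (12.2 to 73.8) |
| 4 | 4 | 0% (0 to 30.8) | 40% (12.2 to 73.8) |

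For *n* = 20 with *x* = *y* = 1, the figures are 0% (0 to 16.8) against 5% (0.1 to 24.9).

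**Step 4. What the documents give for *x* and *y*.** Protocol 3.6 reports early failure in three patients (42%) at 10 mg in an earlier study. That would be 3/7 = 42.9% if the group was 7, which is an assumption. Neither the timing of those failures nor the definition used is stated, so *x* = 4 of 10 is an upper illustration. No clearance rate on Coartem rescue is given, so *y* is unknown. From a 24 h failure to the 48 h film leaves 24 h on rescue, and from a 36 h failure 12 h.

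**The case against.** **Nothing says that counts after rescue are used.** This is correct. A reader might infer it from the word uncorrected, but there that means without PCR correction. The use of such counts follows from the absence of a rule combined with the analysis-set, missing-data and closest-measurement rules. The defect is an unstated rule, not a stated error.

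**Two of the three time points are hardly touched, and many early failures not at all.** This also stands, for the reasons in Step 1.

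**The variable is minor and the failure stays visible.** It is absent from the objectives and endpoints tables, carries no hypothesis and is not compared with Coartem. The same patient is counted in the early-failure proportion, and rescue medication is summarised by arm (SAP 2.4.2). This limits the importance of the point. It does not answer it, because neither summary shows how many negative 48 h films followed rescue.

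**Observed status by assigned arm is a legitimate summary.** It is, provided it is labelled as such; that argues for keeping it as a second line. It is also fair to object to counting every rescued patient as parasitaemic. The 24 h clinical criterion does not require parasites, and rescue after a twice-vomited dose is not parasitological failure. A rule tied to the last film before rescue avoids relabelling patients whose film was already negative.

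**Conclusion.** The gap is real and narrow. Applied literally, the plan tabulates a KAE609 patient rescued before the 48 h film and negative at 48 h as parasite-free under KAE609, while the clearance time censors that patient at rescue. The effect is *y*/*n*: 10 points per patient in an arm of 10, 5 points in an arm of 20, and zero if no rescued patient clears by 48 h.

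A reader might go further and infer that all three time points are biased, that the low-dose arms are understated by 20 to 40 points, or that the dose-response is flattened. The documents do not support these readings. The first fails on the timing of the criteria and the mandatory film before rescue. The second assumes that all early failure occurs before 48 h and that half or all of it clears on rescue. The third needs the same unknown quantities. What can be said is that any effect favours KAE609 and cannot be seen from the table as planned.

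**What to change.** In SAP 2.7.2.2, state that a patient who received rescue antimalarial treatment before a time point is classified at that time point by the last film before rescue: parasitaemic if that film was positive, not otherwise. Show the number rescued before each time point in each arm. Keep the observed-count proportion as a second, labelled line.

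The cost is a short SAP paragraph and a little more programming. The clearance-time rule already needs the time of first rescue, so no new data are required and no clinical rule changes. The 48 h figure in low-dose arms may look less favourable. A patient rescued very early, for example after a twice-vomited dose, would be classified from an early film that is probably positive; the count of rescued patients and the observed line let a reader see this. The SAP's document history records an update after database lock, so if this change is also made after lock it should be labelled as such.

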### **Handling of missing values/censoring/discontinuations**

Patients whose outcome status cannot be determined due to incomplete/missing data will be excluded from analysis. Especially, the denominator is the number of patients who experience treatment failure or have malaria blood film result at Day 29 for LCF and LPF. Patients with ETF will be excluded from the analysis of LCF and patients with ETF or LCF will be excluded from the analysis of LPF.

### **2.7.2.3 Parasite clearance time (PCT) and fever clearance time (FCT)**

Descriptive statistics (mean, standard error, median, quartiles) will be presented for each treatment by cohort using the Kaplan-Meier method. Kaplan-Meier curves will be provided.

PCT will be calculated based on uncorrected parasite counts.

PCT, and FCT will be summarized descriptively by the following subgroup

- Sex (male vs female)

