9.5.1.3 Parasite clearance time (PCT) and fever clearance time (FCT)

Descriptive statistics (mean, standard error, median, quartiles) will be presented for each treatment by cohort using the Kaplan-Meier method. Kaplan-Meier curves will be provided.

PCT will be calculated based on uncorrected parasite counts. Patients without parasite clearance for whatever reason will be censored at the time of last parasite assessment. Patients who were enrolled on the basis of history of fever and did not subsequently have a fever at pre-dose will not be included in the analysis of FCT. Patients without fever clearance for whatever reason will be censored at the time of last temperature assessment. In case that a patient receives rescue medication before (parasite or fever) clearance, the time to event will be censored at the first use of rescue medication.

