## 2 Statistical methods

### 2.1 Data analysis general information

Data will be analyzed by [REDACTED] on behalf of Novartis for the interim safety assessment and after final DBL using SAS version 9.4 according to the data analysis presented in section 9 of the study protocol which will also be available in [Appendix 16.1.1 of the CSR](#). Important information is given in the following sections and details will be provided, as applicable, in [Appendix 16.1.9 of the CSR](#).

At the end of trial, full statistical analyses will be performed by cohort and treatment group. Coartem data from all cohorts will also be pooled.

Any data analysis carried out independently by the investigator should be submitted to Novartis before publication or presentation.

Data analyses required for the study SRC meeting will be analyzed by the third party vendor ([REDACTED]). The outline of the SRC Review analysis plan is presented in the SRC charter and will be detailed in the SRC TFL shells. A separate SAP for SRC is not needed since the statistical methods for SRC are same as those in this SAP.

Information on visit windows, imputation rules and the methods of efficacy and safety analyses is given in the sections to follow and details will be provided, as applicable, in [Appendix 16.1.9 of the CSR](#). This SAP covers the methods for both planned interim safety review and the final analysis.

Unless otherwise stated, summary tables/figures/listings will be on all patients included in the population under consideration.

Categorical data will be presented as frequencies and percentages. For continuous data, n, mean, standard deviation, median, 25th and 75th percentiles, minimum, and maximum will be presented. Additionally, geometric mean will be presented for PK parameters which may be better described using the lognormal distribution.

Unless otherwise stated, p-values will be provided for two-sided alternative hypotheses and presented with up to 4 significant digits after decimal place; confidence intervals will be presented with up to 2 significant digits after decimal place.

Since the randomization is not stratified, statistical analysis will not be stratified. For pooled analyses, coartem patients will be pooled from all the cohorts and compared with patients from different KAE doses.

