#### 2.1.1 General definitions

**Study treatment:** KAE609 is the investigation treatment whereas Coartem® will serve as control. They are referred to as study treatments in the document.

Summary results will be presented by cohort and treatment group. Besides, a pooled Coartem group from all cohorts will be presented from all tables as applicable. The following abbreviated treatment group labels will be used as the column headers in the CSR outputs:

- KAE609 10 mg SD

- KAE609 10 mg QD 3 days
- KAE609 25 mg SD
- KAE609 25 mg QD 3 days
- KAE609 50 mg SD
- KAE609 50 mg QD 3 days
- KAE609 75 mg SD
- KAE609 150 mg SD
- KAE609 225 mg SD or KAE609 110 mg SD
- Coartem
- Pooled Coartem

**Baseline:** The last measurement made prior to and including administration of the first dose of study treatment. Note this may include measurements taken on the day of randomization (e.g. lab, ECG, vital signs). If a patient did not receive any dose of study treatment then the randomization date will be used as the date of first dose of study treatment.

**Study day:** Study day will be calculated with respect to the first dose of study treatment. The first day of administration of study treatment (first dose) is defined as Day 1. Day -1 will be the day before Day 1. Day 0 does not exist. If a patient did not receive any dose of study treatment then the randomization date will be used as the date of first dose of study treatment.

For assessments collected on or after Day 1, study day = date of assessment – date of first dose of study treatment + 1.

For assessments collected prior to Day 1, study day = date of assessment - date of first dose of study treatment.

At the end of trial, full statistical analyses will be performed by cohort and treatment group. Coartem data from all cohorts will also be pooled.

Tail of KM plots: Since the tail of KM plots after the day of last planned assessment is not reliable due to small numbers of patients at risk, the time to event will be truncated to the planned last day (Day 29) regardless of censoring.

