#### 5.5.3 Other secondary/██████████ analysis

##### Kaplan-Meier estimates

An estimate of the survival function in each treatment group will be constructed using Kaplan-Meier (product-limit) method as implemented in PROC LIFETEST with METHOD=KM option. The PROC LIFETEST statement will use the option CONFTYPE=LOGLOG.

Median survival for each treatment group will be obtained along with 95% confidence intervals calculated from PROC LIFETEST output using the method of [[Brookmeyer and Crowley 1982](#)]. Kaplan-Meier estimates of the survival function with 95% confidence intervals at specific time points will be summarized. The standard error of the Kaplan-Meier estimate will be calculated using Greenwood’s formula [[Collett 1994](#)].

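### The Kaplan-Meier mean for parasite and fever clearance time has no common upper limit, so arm means are not comparable and an arm with failures can look faster

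*SAP*

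**What the plan says.** SAP 2.7.2.3 sets the summary for both endpoints: "Descriptive statistics (mean, standard error, median, quartiles) will be presented for each treatment by cohort using the Kaplan-Meier method". Protocol 9.5.1.3 has the same rule, and the data analysis entry of the protocol summary repeats it.

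Failures to clear are censored, never counted as uncleared to a fixed time:

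- For parasites, Protocol 9.5.1.3: "Patients without parasite clearance for whatever reason will be censored at the time of last parasite assessment".
- For fever, the missing-value rules under SAP 2.7.2.3: "Patients without fever clearance for whatever reason will be censored at the time of last temperature assessment".
- For rescue before clearance, the same place: "the time to event will be censored at the first use of rescue medication".

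SAP 2.1 names SAS 9.4. SAP 5.5.3 says the curve is estimated "as implemented in PROC LIFETEST with METHOD=KM option". It then describes the median, the survival estimates at given times and their standard errors. It gives no upper limit for the mean. The only time limit is in SAP 2.1.1, in a note on the tail of the plots: "the time to event will be truncated to the planned last day (Day 29) regardless of censoring".

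**The concern.** A Kaplan-Meier mean is the area under the estimated curve. It is fully determined only if the curve reaches zero, that is, if the longest time in the arm is a clearance. If the longest time belongs to someone who never cleared, the area has to be cut off somewhere. With no stated limit, the cut-off comes from that arm's own data, and the printed standard error belongs to that arm-specific quantity.

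PCT and FCT are named secondary endpoints. SAP 2.1.1 shows results by cohort and treatment beside a pooled Coartem column, and SAP 2.7.2.3 splits these summaries by sex. In arms of 10 or 20, one censored patient can set the cut-off. Failures are plausible at the low doses: Protocol 3.1 expects sub-therapeutic efficacy in the first two cohorts, and Protocol 3.6 cites early failure in three patients (42%) at 10 mg in an earlier study. No between-arm test is planned, so readers will compare the printed summaries by eye.

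**Working it through.** The documents state no expected clearance time, so there is no figure to reproduce. All clearance times below are assumptions, placed on the parasite-count time points of SAP Table 5-6. The arm size of 10 is that of the KAE609 arms in Cohorts 1 and 2.

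Mean to limit L = area under S(t) from 0 to L = sum of (height × width).

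**1. Arm with failures.** Six clear at 8, 12, 12, 24, 24 and 24 h. Four never clear and are censored at 24, 36, 36 and 72 h. S = 1 to 8 h, 0.9 to 12 h, 0.7 to 24 h, then 0.4. No clearance follows 24 h, so the curve is the same if all four are followed to 72 h. This example therefore does not depend on early rescue.

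- Area to the last clearance (24 h): 8 + 0.9×4 + 0.7×12 = 8 + 3.6 + 8.4 = 20.0 h.
- Area to 72 h: 20.0 + 0.4×48 = 39.2 h.

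**2. Arm with late clearance.** The same six, and the other four clear at 48, 60, 72 and 72 h. Mean = (104 + 252)/10 = 35.6 h. The curve reaches zero, so any limit of 72 h or more gives the same value.

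**3. Effect of the unstated limit.** The documents do not say which convention the software applies, so both are shown.

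| Where the area stops | Arm with failures | Late-clearing arm |
|---|---|---|
| Last clearance in the arm | 20.0 h | 35.6 h |
| Last observation, if that is 48 h in the failing arm | 20.0 + 0.4×24 = 29.6 h | 35.6 h |
| Last observation, if that is 72 h in the failing arm | 39.2 h | 35.6 h |
| Common 72 h | 39.2 h | 35.6 h |

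In the first row the arm with 40% failure looks 15.6 h faster.

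**4. An arm of 20.** Eight clear at 12 h, eight at 24 h, four are slow. If the four clear at 60 h: (96 + 192 + 240)/20 = 26.4 h. If they never clear, the area to the last clearance is 12 + 0.6×12 = 19.2 h. With stated limits of 72, 168 and 672 h (Day 29), the failing arm gives 19.2 + 0.2×48 = 28.8 h, 19.2 + 0.2×144 = 48.0 h and 19.2 + 0.2×648 = 148.8 h. The order is now right, but the value depends on the limit, so it must be fixed in advance.

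**5. The direction can reverse.** In step 1, move one 24 h clearance to 72 h and censor all four failures at 72 h. Area to the last clearance: 8 + 3.6 + 8.4 + 0.5×48 = 44.0 h. The matching late-clearing arm: (152 + 252)/10 = 40.4 h. The failing arm is now the slower one.

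**6. A common limit alone does not repair early rescue.** Six clear at 8, 12, 12, 24, 24 and 36 h; four are rescued and censored at 24 h. After 24 h S = 0.5, one patient is left at risk, and the curve falls to zero at 36 h. Mean = 20.0 + 0.5×12 = 26.0 h for every limit of 36 h or more. If the four clear at 48, 60, 72 and 72 h, the mean is (116 + 252)/10 = 36.8 h. Counting the four rescued patients as uncleared to 72 h gives 20.0 + 0.5×12 + 0.4×36 = 40.4 h, which restores the order.

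**7. What the other summaries show.** In steps 1 and 2 the median is 24 h in both arms. The third quartile is not reached with failures and is 60 h with late clearance. In step 6, with censoring at rescue, the third quartile is 36 h although 4 of 10 never cleared, so the proportion cleared (6/10) is needed beside the quartiles.

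**The case against.** A reader might infer that an arm with failures always shows the shorter mean, or that the method systematically favours the arms with most failures. The documents do not support that. Step 5 shows the reverse. Stopping at the last clearance is a software convention that neither document states, and if the area runs to the last observation the order depends on when failures are censored (step 3). What the documents establish is narrower: the limit is unspecified and can differ by arm.

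The consequence is also limited. SAP 2.7 plans no comparison with Coartem for secondary variables, and decisions on dose rest on ALT/AST and narratives. Median, quartiles and curves accompany the mean. Early failure and parasitaemia at 12, 24 and 48 h are reported with confidence intervals. The evidence on failures is thin: three patients as 42% implies about 7 in the group (3/0.42), and one as 25% implies 4. Protocol 3.6 also reports no early failures at 15 or 30 mg, and this trial has no 20 mg arm. The cited rates bear mainly on the two 10 mg arms.

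These points temper the wording and the severity. They do not remove the defect. The Day 29 cap does not either: it shortens long times but does not extend the area in an arm whose last clearance is at 24 h.

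**Conclusion.** The point stands in a limited form. The plan commits to a Kaplan-Meier mean and standard error, censors patients who do not clear, and sets no common limit. When the longest time in an arm is censored, the mean covers an arm-specific range and cannot be compared with other doses or with Coartem. An arm with failures can then appear faster: 20.0 against 35.6 h with 4 of 10 failing, and 19.2 against 26.4 h with 4 of 20.

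Those sizes rest on assumed clearance times and on stopping the area at the last clearance. That the means are not comparable does not depend on the choice between the two conventions. The issue disappears in any comparison of arms where every patient clears. Severity is minor to moderate, because the endpoint is secondary and descriptive.

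**What to change.** Preferred: in SAP 2.7.2.3 delete the Kaplan-Meier mean and standard error for PCT and FCT. Keep the planned median, quartiles and curves, print unreached quartiles as not estimable, and add the proportion of patients cleared in each arm.

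If a mean is kept: report a restricted mean to one pre-specified limit for all arms, for example 72 h, where the close sampling in SAP Table 5-6 ends. Count uncleared or rescued patients as uncleared to that limit. This fits the endpoint in Protocol Table 2-1, which concerns clearance before rescue. Status at 72 h should be known for nearly everyone, because patients stay in hospital to Study Day 4.

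The same wording stands in Protocol 9.5.1.3 and the protocol summary. Changing it there needs an approved amendment under Protocol 11.1. Otherwise list the departure in SAP section 4, which now records no changes. The latest SAP update is dated after database lock, so mark the change as made after lock. Apart from an amendment, the cost is a few lines of SAP text and a small change to table shells and one program. No new data are needed.
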